7.6 RANDOMISATION

The trial will be performed as a double-blind design with respect to placebo and empagliflozin. Patients will be randomised to the trial treatments in a 1:1 ratio. No stratification will be performed in this trial.

Patients will be randomised in blocks to double-blind treatment via an IRT system. Approximately equal numbers of patients will be randomised to each treatment group.

BI will arrange for the randomisation and the packaging and labelling of trial medication. The randomisation list will be generated using a validated system, which involves a pseudo-random number generator so that the resulting treatment will be both reproducible and non-predictable. The block size will be documented in the Clinical Trial Report. Access to the codes will be controlled and documented.

7.7 DETERMINATION OF SAMPLE SIZE

In clinical studies, 30-50 meters have been variably reported as a meaningful distance achieved as a result of therapy [[R17-1227](#)].

The standard deviation (SD) of 72 m is assumed for sample size considerations of this trial [[R17-1225](#)]. The risk of observing a higher SD in this trial will be mitigated by using duplicate measurements of 6MWT at baseline, Week 6 and Week 12 [[R17-2791](#)]. For non-missing values a normal distribution for change from baseline in distance walked in 6 minutes is assumed in all below sample size estimations.

The trial is designed to achieve a power of 90% for a two sided test at level $\alpha = 0.05$ to detect a difference between empagliflozin and placebo.

Using a normal distribution to calculate the probability that an observation X in Empagliflozin group will be less than an observation Y in the control group under the alternative, the following table presents the number of required evaluable patients for different assumed means of absolute difference in distance walked within 6 minutes as obtained by using the Wilcoxon sample size estimation procedure from commercial software nQuery Advisor® 7.0 statistical package by Statistical Solutions Ltd.

Table 7.7: 1 Sample size calculation

True treatment difference in distance walked in 6 minutes	SD	P(X<Y)	Required number of patients per group
30 m	72 m	0.384	131
40 m	72 m	0.347	76
50 m	72 m	0.312	50

A true treatment difference of 30 m is used as a conservative measure for sample size calculation to ensure that the study could detect the lowest effect size reported to be meaningful.

Therefore, a total of 131 evaluable patients per group are needed in order show a significant result for a two-sided test at level $\alpha = 0.05$ with a power of 90% not considering missing data.

To assess the impact of missing data a simulation with 100000 iterations was performed. A normal distribution for 6MWT distance was assumed and a total of 5%, 8% and 10% patients imputed to worst case as outlined in [section 7.5](#) in each treatment group were investigated. The results are summarized in [table 7.7: 2](#).

Table 7.7: 2 Simulation of imputation rules

N per group	Simulated true treatment difference for non-missing data [mean \pm SD]	Percentage of missing data imputed to worst case	Power
150	30 \pm 72	5%	90%
150	30 \pm 72	8%	87%
150	30 \pm 72	10%	85%

Therefore, a total of 150 patients per treatment group will allow for a drop-out and imputation of about 5% of the patients in order to show a significant result for a two-sided test at level $\alpha = 0.05$ with a power of 90%. With a drop-out rate of 10%, a total of 150 patients per treatment group would still yield a power of 85%.

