7.3.1 Primary endpoint analyses

The primary endpoint ‘change from baseline to week 12 in exercise capacity’ will be evaluated using a normal approximation of the Wilcoxon rank test using the randomized set. For estimation of effect the non-parametric Hodges-Lehmann estimate for the median difference will be calculated. Any confirmatory conclusion such as for hierarchical testing will be based on the result of the Wilcoxon rank test and will not consider the Hodges-Lehmann estimate or the corresponding confidence interval, which are given to support interpretation.

If repeated distance walked in 6 minutes (6MWT) measurements on the same day are available the longest distance will be used for this day.

Change from baseline will be defined as distance walked in 6 minutes (6MWT) at week 12 assessment minus the distance walked at baseline.

If no value for the 6MWT is available at week 12, an imputed value as defined in [table 7.5: 1](#) will be used.

Sensitivity analysis for the primary endpoint will include using a mixed model repeated measure analysis (MMRM) with baseline 6MWT as a covariate without imputation of missing values.

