7.5 HANDLING OF MISSING DATA

Patients with an available week 12 measurement of the 6MWT, regardless of whether on or off-treatment, will be ranked based on change from baseline in 6MWT distance at week 12.

If a patient performs the visit at week 12 but is unable to walk or unable to perform the 6MWT due to safety concerns, then this will be noted accordingly in the case report form and will not be regarded as missing data. This case will be evaluated as a measured distance of 0m.

Missing data will be imputed according to the rules outlined in [table 7.5: 1](#), and ranks will be assigned based on the imputed data. Imputed data will also be used to calculate the Hodge Lehmann estimates for the median difference. Note that no imputation will be used in the MMRM analysis that serves as sensitivity analysis in this trial.

All imputed data due to missing data will be lower than measured values. The lowest measurable value of the primary endpoint of change from baseline in 6MWT distance is a reduction by 350m, i.e. the highest possible baseline value (350 m), and at week 12 the lowest possible value of 0m. Therefore, all imputed values for change from baseline for patients with missing walking distance at week 12 are below -350 m.

Table 7.5: 1 Imputation rules for missing primary endpoint

	Category	Ranking	Case description	Imputed change from baseline in 6MWT for described case (in m)*
1	Missing data on 6MWT at week 12 and no clinical event: Patients with missing 6MWT at week 12 and no event as in category 2 or 3	If post-baseline value is available, rank by last available value. Rank below if no post-baseline value is available	Patient has a change from baseline to last available value of x m, no clinical event	-352 +x/1000
			No information of post-baseline 6MWT distance and no clinical event	-354
2	Missing data and clinical event (except death). A clinical event is defined as ongoing SAE or AE leading to treatment discontinuation and patient is alive at week 12	Ranked above patients who died, but below patients with missing data and no clinical event.	Patient has ongoing SAE or AE leading to treatment discontinuation, no information of week 12 6MWT distance and patient alive at week 12.	-356
3	Patient died before the measurement of 6MWT at week 12 was conducted.	Ranked by time to death from randomization	Patient died y days after randomization	-358+y/1000

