7.7.1 Power estimation for key secondary endpoints

KCCQ

For power estimation of the KCCQ TSS a treatment difference of 5 points is assumed. In patients with heart failure previous studies have reported a standard deviation of the KCCQ TSS between 13 in the CONFIRM-HF trial and 19-21 in the FAIR-HF trial [[R17-1226](#), [R17-3097](#)].

Using a normal distribution to calculate the probability that an observation X in Empagliflozin group will be less than an observation Y in the control group under the alternative, a sample size of 150 per treatment group will result in approximately 55% to 90% power to detect a 5 point difference between treatment groups at an alpha-level of 5% using a Wilcoxon test, if all questionnaires are available at the end of the trial (see [table 7.7.1: 1](#)).

Due to the Hochberg procedure, if CHQ dyspnea is not significant, an alpha-level of 2.5% will become applicable. [Table 7.7.1:1](#) therefore additionally shows an alpha-level of 2.5 %.

Table 7.7.1: 1 Power Estimation for KCCQ TSS

SD	P(X<Y)	Power for $\alpha = 5\%$	Power for $\alpha = 2.5\%$
13	0.393	89%	83%
15	0.407	79%	71%
17	0.418	69%	59%
20	0.430	55%	44%

While every effort will be made to collect the questionnaire for randomized patients regardless of being on or off treatment, about 5% missing questionnaires may be assumed and are considered for power evaluation in analogy with the primary endpoint.

Results of a simulation of the power with 100000 iterations to detect a 5 point difference between treatment groups in a Wilcoxon test with imputation rules analogously to the primary endpoint, assuming 5% missing questionnaires at week 12 in each treatment arm, a normal distribution for non-missing scores, and alpha of 5% is summarized in the [table 7.7.1:2](#) below.

Table 7.7.1: 2 Simulation of Imputation Rules for KCCQ TSS

SD	Power for $\alpha = 5\%$	Power for $\alpha = 2.5\%$
13	85%	76%
15	73%	61%
17	61%	49%
20	47%	35%

Overall power is reasonable to evaluate superiority of empagliflozin versus placebo assuming a treatment effect of 5 points and a standard deviation that does not exceed 15 points.

CHQ

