For power estimation of the CHQ dyspnea a treatment difference of 0.5 points is assumed [R99-1220]. CHQ and CRQ (an instrument almost identical to CHQ used in respiratory disease) are reported as performing similarly [R99-1220]. A standard deviation of the change from baseline of the standardized CRQ dyspnea score of 1.15 has been reported [R05-1404]. Similar data were also reported for CHQ [R17-2917]. Therefore, for power estimation, a standard deviation of 1 to 1.4 is assumed.

Using a normal distribution to calculate the probability that an observation X in Empagliflozin group will be less than an observation Y in the control group under the alternative, a sample size of 150 per treatment group will result in approximately 84% to 98% power per score to detect a 0.5 point difference between treatment groups at an alpha-level of 5% using a Wilcoxon test, if all questionnaires are available at the end of the trial (see [Table 7.7.1:3](#)).

Due to the Hochberg procedure, if KCCQ-TSS is not significant, an alpha-level of 2.5% will become applicable. [Table 7.7.1: 3](#) therefore additionally shows an alpha-level of 2.5 %.

Table 7.1.1: 3 Power Estimation for CHQ-SAS

SD	P(X<Y)	Power for $\alpha = 5\%$	Power for $\alpha = 2.5\%$
1	0.362	98%	97%
1.2	0.384	93%	89%
1.4	0.400	84%	77%

While every effort will be made to collect the questionnaire for randomized patients regardless of being on or off treatment, about 5% missing questionnaires may be assumed and are considered for power evaluation in analogy with the primary endpoint.

Results of a simulation of the power with 100000 iterations to detect a 0.5 point difference between treatment groups in a Wilcoxon test with above imputation rules, assuming 5% missing questionnaires at week 12 in each treatment arm, a normal distribution for non-missing scores, alpha of 5% is summarized in the [table 7.7.1: 4](#) below.

Table 7.1.1: 4 Simulation of Imputation Rules for CHQ-SAS

SD	Power for $\alpha = 5\%$	Power for $\alpha = 2.5\%$
1	98%	95%
1.2	90%	83%
1.4	79%	69%

Overall a power of approximately 70% or higher is expected to detect a difference of 0.5 for each score given the planned sample size of 150 patients per treatment group.

Calculations were performed using nQuery Advisor® 7.0 statistical package by Statistical Solutions Ltd and simulation was performed using R version 3.3.2 by The R Foundation for Statistical Computing.

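### The 85% power quoted for a 10% drop-out rate holds only if both arms lose the same number of patients; averaged over chance imbalance it is about 81%

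*Protocol*

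**What the plan says.** Protocol 7.7 sets the target: "The trial is designed to achieve a power of 90% for a two sided test at level" 0.05, for a 30 m difference and an SD of 72 m. This needs 131 evaluable patients per group. A simulation of 100,000 iterations then examines missing data, with "a total of 5%, 8% and 10% patients imputed to worst case" in each treatment group. For 150 per group, Table 7.7:2 gives power of 90%, 87% and 85%. The closing paragraph of 7.7 turns the last row into a statement about a rate: "With a drop-out rate of 10%, a total of 150 patients per treatment group would still yield a power of 85" per cent.

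The test is specified in Protocol 7.3.1: the primary endpoint is "evaluated using a normal approximation of the Wilcoxon rank test using the randomized set". Protocol 7.5 places every imputed change below -350 m, and so below every measured change. Discontinuing treatment does not by itself trigger imputation: "Patients with an available week 12 measurement of the 6MWT, regardless of whether on or off-treatment, will be ranked based on change from baseline". On allocation, Protocol 7.6 says "Approximately equal numbers of patients will be randomised to each treatment group". Section 7.7.1 makes the same kind of calculation for KCCQ-TSS and CHQ-SAS dyspnea, "assuming 5% missing questionnaires at week 12 in each treatment arm".

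**The concern.** A percentage missing in each arm and a drop-out rate are different conditions. Under the first, both arms lose exactly the same number of patients in every simulated trial. Under the second, each arm's count is random even when the true rate is the same. At 10% the between-arm difference in missing counts has SD √(2 × 150 × 0.1 × 0.9) = 5.2 patients. Blocked 1:1 allocation balances the arm sizes but not these counts.

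This matters because of the imputation rule. A missing patient takes a bottom rank, so one extra missing patient in an arm moves the Wilcoxon statistic about as far as a single patient can. Holding the counts equal removes that source of variance. At stake is the reassurance the 8% and 10% rows give about worse-than-planned missingness, not the validity of the test.

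The word drop-out adds a smaller problem. Patients who stop treatment but walk at week 12 are ranked on their observed change, so the quantity that drives power is missing week-12 6MWT data.

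**Working it through.** **Inputs.** From Protocol 7.7: 150 per arm, difference 30 m, SD 72 m, normal non-missing changes, two-sided 5%, missing 5%, 8% and 10%. From 7.3.1: Wilcoxon test, normal approximation. From 7.5: imputed values rank below all measured values. Assumption not in the documents: for the per-patient runs, missingness is independent, with equal true rates in both arms.

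**1. Base case.** P(X<Y) = Φ(−30/(72√2)) = 0.384. Noether's formula gives n = (1.960 + 1.282)² / (6 × 0.11586²) = 130.5, so 131 per group, as in Table 7.7:1.

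**2. Simulation** (100,000 iterations per setting, continuity-corrected). Power with no missing data is 94.0%.

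| Missing | Protocol | Equal fixed counts per arm | Per-patient missingness | Null rejection, per-patient |
|---|---|---|---|---|
| 5% | 90% | 90.0% (8/8) | 88.5% | 4.95% |
| 8% | 87% | 87.3% (12/12) | 83.9% | 4.92% |
| 10% | 85% | 85.0% (15/15) | 80.8% | 4.93% |

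Equal fixed counts reproduce all three stated figures. A separate set of 40,000 runs per setting, without continuity correction, gave 84.7–84.8% (fixed) and 80.8–80.9% (per-patient) at 10%. Fixing the overall total missing and splitting it at random between arms gave 80.7–81.1%. Tied or distinct imputed values made no material difference.

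**3. Hand check.** Work with the proportion of between-arm pairs in which the empagliflozin patient ranks higher, minus one half.

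- Null SE: √(301/(12 × 150²)) = 0.03339. Significance needs an excess of 1.96 × 0.03339 = 0.06544.
- Expected excess at 10% missing: 0.9² × 0.11586 = 0.09385.
- Counts fixed at 15/15: only the 135 v 135 comparison varies, with SE √(135² × 271/12)/150² = 0.02851. Power ≈ Φ((0.09385 − 0.06544)/0.02851) = Φ(0.996) = 84.0%.
- Counts random: the excess changes by −(0.9 × 0.61586 + 0.05) = −0.6043 per unit of the missing proportion on empagliflozin, and by +(0.9 × 0.38414 + 0.05) = +0.3957 on placebo. Each proportion has variance 0.1 × 0.9/150 = 0.0006. The added SE is √(0.0006 × (0.6043² + 0.3957²)) = 0.01769, and the total SE is √(0.02851² + 0.01769²) = 0.03356. Power ≈ Φ(0.02841/0.03356) = Φ(0.847) = 80.1%.

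The approximation runs about one point below the simulation, but it gives the same loss of about 4 points. The total SE (0.03356) is close to the null SE (0.03339): the test's reference variance already allows for chance placement of the bottom ranks. That is why size holds under random missingness.

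**4. Power for given splits at 10%** (50,000 iterations each).

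| Missing, empagliflozin/placebo | Power |
|---|---|
| 13/17 | 93% |
| 14/16 | 90% |
| 15/15 | 85% |
| 16/14 | 78% |
| 17/13 | 71% |

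A two-patient shift in the split (16/14 or 14/16) loses 7 points one way and gains 5 the other; a four-patient shift loses 14 and gains 8. Averaging over splits therefore brings power below 85%.

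**5. Key secondary endpoints at 5% missing**, per-patient, power at alpha 5%/2.5%, protocol value in brackets.

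| Endpoint, SD | Per-patient | Protocol |
|---|---|---|
| KCCQ-TSS, 13 | 83/75 | (85/76) |
| KCCQ-TSS, 15 | 72/61 | (73/61) |
| KCCQ-TSS, 17 | 61/49 | (61/49) |
| KCCQ-TSS, 20 | 48/37 | (47/35) |
| CHQ dyspnea, 1 | 97/94 | (98/95) |
| CHQ dyspnea, 1.2 | 88/82 | (90/83) |
| CHQ dyspnea, 1.4 | 77/68 | (79/69) |

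The higher-power rows fall by about 1–2 points. The low-power KCCQ rows stay level or rise slightly.

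**The case against.** The strongest reply is that nothing was miscalculated. Table 7.7:2 states its scenario, a percentage missing in each group, and is right for it; 85% is the power when each arm has its expected number missing. That is true of the table. It does not rescue the closing sentence, which offers the figure as the power at a rate, without the condition.

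The protocol also does not say how missingness was drawn, so fixed equal counts are an inference. That stands as a caveat. It is nevertheless the only scheme tested that returns all three stated powers; random missingness misses the 8% and 10% rows by 3 to 4 points.

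The replacement figures are conditional as well. They assume equal true rates, whereas two of the imputation categories depend on adverse events and deaths, which may differ by arm. The split table shows that a modest difference in rates could move power by more than 4 points. This is a fair point, and the assumption must be printed with the restated figures.

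Finally, the sample size rests on the 5% row, where the gap is about 1.5 points, and no secondary-endpoint cell moves by more than about 2. This stands too. It limits the finding to the robustness figures and makes rerunning the secondary tables a matter of consistency.

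**Conclusion.** The concern holds. Under the plan's own worst-rank rule and planning values, average power at 10% missing week-12 data is about 81%, not 85%. At 8% it is about 84%, not 87%; at the 5% planning case it is about 88.5%, not 90%. At 10%, the chance of missing a true 30 m effect rises from 15% to about 19%.

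These figures rest on normal non-missing changes, independent missingness and equal true rates in both arms. An individual trial's split may put its power above or below 85%; the average is what falls. The stated power should be corrected.

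**What to change.** - Rerun the existing simulation with missingness drawn patient by patient, and restate Table 7.7:2 as about 88–89%, 84% and 81%. State beside it that the true missing rate is assumed equal in both arms.
- Reword the closing paragraph of Protocol 7.7 so that it refers to missing week-12 6MWT data instead of drop-out, and gives about 81% at 10%. If the 85% is kept, say that it assumes equal missing counts in the two arms.
- For consistency, rerun the simulated powers in 7.7.1 (Table 7.7.1:2 for KCCQ-TSS and the CHQ-SAS table captioned 7.1.1:4) in the same way. Do this row by row, because a flat reduction would be wrong for the low-power KCCQ rows.

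The cost is one rerun of an existing simulation and a few edited figures. The test, missing-data rule, sample size and trial conduct do not change.

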7.7.1 Power estimation for key secondary endpoints

KCCQ

For power estimation of the KCCQ TSS a treatment difference of 5 points is assumed. In patients with heart failure previous studies have reported a standard deviation of the KCCQ TSS between 13 in the CONFIRM-HF trial and 19-21 in the FAIR-HF trial [[R17-1226](#), [R17-3097](#)].

Using a normal distribution to calculate the probability that an observation X in Empagliflozin group will be less than an observation Y in the control group under the alternative, a sample size of 150 per treatment group will result in approximately 55% to 90% power to detect a 5 point difference between treatment groups at an alpha-level of 5% using a Wilcoxon test, if all questionnaires are available at the end of the trial (see [table 7.7.1: 1](#)).

Due to the Hochberg procedure, if CHQ dyspnea is not significant, an alpha-level of 2.5% will become applicable. [Table 7.7.1:1](#) therefore additionally shows an alpha-level of 2.5 %.

Table 7.7.1: 1 Power Estimation for KCCQ TSS

SD	P(X<Y)	Power for $\alpha = 5\%$	Power for $\alpha = 2.5\%$
13	0.393	89%	83%
15	0.407	79%	71%
17	0.418	69%	59%
20	0.430	55%	44%

While every effort will be made to collect the questionnaire for randomized patients regardless of being on or off treatment, about 5% missing questionnaires may be assumed and are considered for power evaluation in analogy with the primary endpoint.

Results of a simulation of the power with 100000 iterations to detect a 5 point difference between treatment groups in a Wilcoxon test with imputation rules analogously to the primary endpoint, assuming 5% missing questionnaires at week 12 in each treatment arm, a normal distribution for non-missing scores, and alpha of 5% is summarized in the [table 7.7.1:2](#) below.

Table 7.7.1: 2 Simulation of Imputation Rules for KCCQ TSS

SD	Power for $\alpha = 5\%$	Power for $\alpha = 2.5\%$
13	85%	76%
15	73%	61%
17	61%	49%
20	47%	35%

Overall power is reasonable to evaluate superiority of empagliflozin versus placebo assuming a treatment effect of 5 points and a standard deviation that does not exceed 15 points.

CHQ

For power estimation of the CHQ dyspnea a treatment difference of 0.5 points is assumed [R99-1220]. CHQ and CRQ (an instrument almost identical to CHQ used in respiratory disease) are reported as performing similarly [R99-1220]. A standard deviation of the change from baseline of the standardized CRQ dyspnea score of 1.15 has been reported [R05-1404]. Similar data were also reported for CHQ [R17-2917]. Therefore, for power estimation, a standard deviation of 1 to 1.4 is assumed.

Using a normal distribution to calculate the probability that an observation X in Empagliflozin group will be less than an observation Y in the control group under the alternative, a sample size of 150 per treatment group will result in approximately 84% to 98% power per score to detect a 0.5 point difference between treatment groups at an alpha-level of 5% using a Wilcoxon test, if all questionnaires are available at the end of the trial (see [Table 7.7.1:3](#)).

Due to the Hochberg procedure, if KCCQ-TSS is not significant, an alpha-level of 2.5% will become applicable. [Table 7.7.1: 3](#) therefore additionally shows an alpha-level of 2.5 %.

Table 7.1.1: 3 Power Estimation for CHQ-SAS

SD	P(X<Y)	Power for $\alpha = 5\%$	Power for $\alpha = 2.5\%$
1	0.362	98%	97%
1.2	0.384	93%	89%
1.4	0.400	84%	77%

While every effort will be made to collect the questionnaire for randomized patients regardless of being on or off treatment, about 5% missing questionnaires may be assumed and are considered for power evaluation in analogy with the primary endpoint.

Results of a simulation of the power with 100000 iterations to detect a 0.5 point difference between treatment groups in a Wilcoxon test with above imputation rules, assuming 5% missing questionnaires at week 12 in each treatment arm, a normal distribution for non-missing scores, alpha of 5% is summarized in the [table 7.7.1: 4](#) below.

Table 7.1.1: 4 Simulation of Imputation Rules for CHQ-SAS

SD	Power for $\alpha = 5\%$	Power for $\alpha = 2.5\%$
1	98%	95%
1.2	90%	83%
1.4	79%	69%

Overall a power of approximately 70% or higher is expected to detect a difference of 0.5 for each score given the planned sample size of 150 patients per treatment group.

Calculations were performed using nQuery Advisor® 7.0 statistical package by Statistical Solutions Ltd and simulation was performed using R version 3.3.2 by The R Foundation for Statistical Computing.

8. INFORMED CONSENT, TRIAL RECORDS, DATA PROTECTION, PUBLICATION POLICY, AND ADMINISTRATIVE STRUCTURE

The trial will be carried out in accordance with the Medical Devices Directive (93/42/EEC) and the harmonised standards for Medical Devices (ISO 14155, current version).

The trial will be carried out in compliance with the protocol, the ethical principles laid down in the Declaration of Helsinki, in accordance with the ICH Harmonized Tripartite Guideline for Good Clinical Practice (GCP), relevant BI Standard Operating Procedures (SOPs), the European Union (EU) regulation 536/2014 and other relevant regulations.

Standard medical care (prophylactic, diagnostic and therapeutic procedures) remains the responsibility of the treating physician of the patient.

The investigator will inform the sponsor immediately of any urgent safety measures taken to protect the trial patients against any immediate hazard, as well as of any serious breaches of the protocol or of ICH GCP.

The Boehringer Ingelheim transparency and publication policy can be found on the following web page: trials.boehringer-ingelheim.com. The rights of the investigator and of the sponsor with regard to publication of the results of this trial are described in the investigator contract. As a rule, no trial results should be published prior to finalization of the Clinical Trial Report. The certificate of insurance cover is made available to the investigator and the patients, and is stored in the ISF.

The Boehringer Ingelheim transparency and publication policy can be found on the following web page: trials.boehringer-ingelheim.com. The rights of the investigator and of the sponsor with regard to publication of the results of this trial are described in the investigator contract. As a rule, no trial results should be published prior to finalization of the Clinical Trial Report. The certificate of insurance cover is made available to the investigator and the patients, and is stored in the ISF.

